### **6. SUBJECT RECRUITMENT & SCREENING**

Fifty subjects will be recruited for the study with an expected attrition rate of 10%. Sample size has been minimized, but is necessary for statistical power and

conclusions. Subjects will be male and female 18 years or older, of all ethnicities, denominations or other social/economical variations. All participants will speak English fluently in order for consent to be performed properly. Baseline pain score will be calculated through a questionnaire in at the urology clinic

Subjects of prospective study will be randomly divided using electronic program into two groups:

- The first group will receive intraoperative local Liposomal Bupivacaine injection at the port placement site.
- The control group will receive will local Marcaine (bupivacaine HCl) injection

Primary Outcome Measures:

- Total opioid consumption measured in intravenous morphine equivalents dose during the postoperative hospital Stay
- Postoperative pain assessment using visual Analog Pain Scores & Brief Pain Inventory form.
- Length of Hospital Stay
- Time to First Opioid Use.
- Postoperative Constipation , paralytic ileus

Time Frame: All data was recorded during the patient's hospital stay. All data will be collected from the electronic medical record, typically within 30 days of discharge from hospital.

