## **8. STUDY DESIGN**

Background or rationale for this study:

Liposomal bupivacaine was developed to extend the duration of efficacy of bupivacaine from the typical 6 - 8 hours up to 72 hours. The prolonged duration of liposomal bupivacaine was initially demonstrated in mice in 1994. Two randomized controlled trials using liposomal bupivacaine for bunionectomy and hemorhoidectomy resulted in FDA approval for its use in humans. More recently, liposomal bupivacaine has also been found to improve pain control for patients undergoing total knee arthroplasty. Infiltration of a local anesthetic into laparoscopic port sites is a common practice that has been shown in some studies to improve postoperative pain. Currently, no standard of care exists for postoperative pain and management is based on surgeon and anesthesiologist preferences. Liposomal bupivacaine has been one form of administered local, long-acting analgesia that

surgical centers have turned to. In addition, the analgesia has fewer adverse effects than opioids, with comparable adverse effects to those seen in bupivacaine alone.

Objectives: A prospective, randomized controlled study to determine the efficacy of liposomal bupivacaine given by local injection at all the wound sites in patients undergoing urologic surgeries.

Procedures involved (Research Interventions):

- The first group will receive intraoperative local Liposomal Bupivacaine injection at the surgical site.
- The control group will receive and will receive local Marcaine (bupivacaine HCl) injection.

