#### **9. DATA COLLECTION**

We will be using electronic medical records to retrieve data from subjects who will undergo urologic surgery and save it in a secured excel file.

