#### **12. RISK AND INJURY**

The safety of EXPAREL was evaluated in 10 randomized, double-blind, local administration into the surgical site clinical studies involving 823 patients undergoing various surgical procedures. Patients were administered a dose ranging from 66 to 532 mg of EXPAREL. In these studies, the most common adverse reactions (incidence greater than or equal to 10%) following EXPAREL administration were nausea, constipation, and vomiting. The common adverse reactions (incidence greater than or equal to 2% to less than 10%) following EXPAREL administration were pyrexia, dizziness, edema peripheral, anemia, hypotension, pruritus, tachycardia, headache, insomnia, anemia postoperative, muscle spasms, hemorrhagic anemia, back pain, somnolence, and procedural pain. The less common/rare adverse reactions (incidence less than 2%) following EXPAREL administration were chills, erythema, bradycardia, anxiety, urinary retention, pain, edema, tremor, dizziness postural, paresthesia, syncope, incision site edema, procedural hypertension, procedural hypotension, procedural nausea, muscular weakness, neck pain, pruritus generalized, rash pruritic, hyperhidrosis, cold sweat, urticaria, bradycardia, palpitations, sinus bradycardia, supraventricular extrasystoles, ventricular extrasystoles, ventricular tachycardia, hypertension, pallor, anxiety, confusional state, depression, agitation, restlessness, hypoxia, laryngospasm, apnea, respiratory depression, respiratory failure, body temperature increased, blood pressure increased, blood pressure decreased, oxygen saturation decreased, urinary incontinence, vision blurred, tinnitus, drug

hypersensitivity, and hypersensitivity. Subject privacy will be protected as subject identifiers will be removed after data collection and before data analysis.

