**13. BENEFIT(S)**

Patient may benefit if you are not in the control group and find less postoperative pain and/or shorter hospital stay. In addition, the information learned from this study will determine if the drug has favorable outcomes on urologic surgeries. Future benefits may be present in improving the pain control after urologic surgeries and improve the overall patients' satisfaction.

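### Nausea and vomiting, two of the three commonest reactions the protocol lists for the test drug, are on no outcome list, and no by-arm safety summary is planned

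*Combined protocol and SAP*

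**What the plan says.** Section 6 has a single outcome list, headed "Primary Outcome Measures". It holds opioid consumption, pain scores, length of stay, time to first opioid, and "Postoperative Constipation , paralytic ileus". The last item has no definition and no stated direction. The public text contains no secondary list and no safety list.

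The objective in section 8 is "A prospective, randomized controlled study to determine the efficacy of liposomal bupivacaine given by local injection at all the wound sites". No safety objective accompanies it. The background in the same section takes as given that "the analgesia has fewer adverse effects than opioids, with comparable adverse effects to those seen in bupivacaine alone"; plain bupivacaine is this trial's control.

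Section 9 describes data collection in one sentence: "We will be using electronic medical records to retrieve data from subjects who will undergo urologic surgery", to be held in a spreadsheet. It names no variables and no adverse-event item. Section 11 directs the analysis to the pain-related outcomes and mentions no safety analysis.

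Section 12 names the commonest reactions "following EXPAREL administration were nausea, constipation, and vomiting", in the band of 10% or more. Hypotension and tachycardia are in its band from 2% to below 10%. It also states that identifiers are removed after data collection and before analysis. Section 13 says that "the information learned from this study will determine if the drug has favorable outcomes on urologic surgeries".

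**The concern.** The protocol itself identifies the three reactions most likely to be seen with the test drug, but arranges to look at only one. Nausea and vomiting are routine postoperative events and matter to any judgement that one local anaesthetic is preferable to another. If they are not named in advance, nobody is told to extract them, and the report can give pain and opioid results without them.

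Two features make this more than untidiness. First, section 13 promises a judgement on whether outcomes are favourable, and section 8 assumes that adverse effects are comparable with those of plain bupivacaine. The trial randomises between exactly those two drugs, so it could at least describe whether that assumption looks reasonable in its own patients. Second, the omission is hard to repair. Once the data set has been stripped of identifiers, going back to the chart for another field is no longer simple.

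A smaller matter concerns the one listed reaction. Constipation may be influenced both by opioid use and by whatever else differs between the arms. The plan does not say how a difference, or the absence of one, is to be read.

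**Working it through.** **1. Reactions set against outcomes**

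| Reaction in section 12 | Band | On the section 6 list? | By-arm summary planned? |
|---|---|---|---|
| Constipation | 10% or more | Yes, with paralytic ileus | Only as a listed outcome |
| Nausea | 10% or more | No | No |
| Vomiting | 10% or more | No | No |
| Hypotension, tachycardia | 2% to below 10% | No | No |

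Sections 9 and 11 do not fill the gap. The first gives a data source without a variable list, and the second covers pain-related outcomes only.

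**2. The plan's only design figure**

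Section 6 gives 50 subjects and 10% expected attrition, so 50 × 0.90 = 45 evaluable. The 50 itself cannot be reproduced, because no alpha, power, effect size, standard deviation or event rate is stated. The allocation ratio is not stated either. I assume 1:1, giving 25 per arm as recruited and 45 / 2 = 22.5 after attrition, taken as 22.

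**3. Would these events be seen at all?**

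P(at least one case in an arm of n) = 1 − (1 − q)^n

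- q = 0.10, n = 22: 1 − 0.90^22 = 0.902
- q = 0.10, n = 25: 1 − 0.90^25 = 0.928
- q = 0.02, n = 22: 1 − 0.98^22 = 0.359
- q = 0.02, n = 25: 1 − 0.98^25 = 0.397

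The 10% and 2% rates are the lower edges of the section 12 bands. If the drug's rates in these patients fall within those bands, the figures are minimum chances for the test arm. Section 12 gives no rate for the control drug.

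**4. Could the arms be separated?**

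Exact power of Fisher's test (two-sided alpha 0.05, assumed) is the sum of Bin(x; n, p1) × Bin(y; n, p2) over all pairs (x, y) with a Fisher p-value of 0.05 or less.

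| True rates | n = 25 per arm | n = 22 per arm |
|---|---|---|
| 10% v 20% | 0.086 | 0.085 |
| 10% v 30% | 0.305 | 0.277 |
| 10% v 40% | 0.591 | 0.546 |

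For 80% power at 10% v 20%, the normal approximation with pooled variance under the null gives

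n = [1.960 × √(2 × 0.15 × 0.85) + 0.842 × √(0.10 × 0.90 + 0.20 × 0.80)]² / 0.10² ≈ 199 per arm.

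An empty cell would not be reassuring either. With no events in n patients, the one-sided 95% upper limit is 1 − 0.05^(1/n), which is 12.7% for n = 22 and 11.3% for n = 25.

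**5. Can the fields be added later?**

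Section 12 removes identifiers before analysis. Section 10 does keep a code linking to identifiers on a secure server but does not say for how long, and section 15 speaks of removal after analysis. Recovery is therefore not ruled out by the text, but it cannot be relied on.

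**The case against.** Several points on the other side stand.

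- **Constipation as efficacy.** A reader might infer that constipation is being scored as an efficacy result, since the only objective is efficacy. The list is headed as primary outcomes, with no efficacy label and no direction, so the documents do not support that.
- **Opposing effects.** A reader might also infer that the drug's own constipating effect would offset opioid sparing within one count. Section 12 gives incidences after administration with no comparator rate, so no excess over plain bupivacaine is shown. The same section lists pain and procedural pain among the reactions, which illustrates that a listing is not evidence of a drug effect. The randomised contrast validly estimates the net difference, and opioid use is measured separately. Moving the same count to a safety heading would separate nothing.
- **No harm data.** It would be too strong to say that the trial would have none. Constipation and ileus are harm data compared between randomised arms. Nor do the documents say that nausea and vomiting will not be extracted; they are simply not listed.
- **Section 13 is not a decision rule.** It is general wording on benefits. It nevertheless states what the study is meant to determine, and a judgement of that kind needs a harm side.
- **Too small to test harms.** True, as the 9% shows. That argues for descriptive reporting, not for omission.
- **Cost.** Collecting every reaction in section 12 would be burdensome, and routine charting would give unreliable counts for many of them. That demand is not justified.

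What remains is the gap between the reactions the protocol names and those it lists for comparison.

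**Conclusion.** The point holds as one of incomplete harm recording. Two of the three reactions that the protocol puts at 10% or more are on no outcome list, and no adverse-event recording or by-arm safety summary is planned in the public text. The comparison of pain and opioid use is unaffected. What is weakened is any statement that the drug's outcomes are favourable.

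On size: with 22–25 per arm, a reaction at 10% has a 90–93% chance of at least one case in an arm, so such events would very probably occur. At 2% the chance is 36–40%. Power for 10% against 20% is about 9%, so recording them would not establish or exclude even a doubling. These figures rest on 1:1 allocation, two-sided alpha of 0.05, and the section 12 rates carrying over to urologic patients; none of these is stated in the plan.

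This is a cheap improvement to make before data collection, not a flaw that invalidates the design.

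**What to change.** In section 6, add a short tolerability list, extracted from the same electronic record over the same hospital stay in both arms: nausea, vomiting, antiemetic use, and charted hypotension and tachycardia. State how each item is identified in the record. Add the fields to section 9.

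In section 11, state that these items are reported descriptively by arm (counts and percentages, without significance tests), in one table with constipation and ileus, and that the table accompanies any conclusion that outcomes are favourable. State also that the constipation/ileus result is the net difference between arms, to be read in either direction.

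Make the change before identifiers are removed.

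The cost is a few extra extraction fields and one table. Charted events are prone to under-recording, so the counts should be presented with that caution. The other reactions named in section 12 need not be collected item by item.

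### Constipation and ileus are recorded only during the hospital stay, itself a primary outcome, so at equal risk the arm discharged earlier can be expected to show fewer events

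*Combined protocol and SAP*

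**What the plan says.** Section 6 lists five primary outcome items. One is "Postoperative Constipation , paralytic ileus" and another is "Length of Hospital Stay". Neither bowel event has a definition, an assessor or a window of its own.

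Two sentences under Time Frame apply to all outcomes. The first is "All data was recorded during the patient's hospital stay". The second is "All data will be collected from the electronic medical record, typically within 30 days of discharge from hospital".

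Section 13 says that a patient outside the control group may "find less postoperative pain and/or shorter hospital stay". Section 9 gives the source: "We will be using electronic medical records to retrieve data from subjects who will undergo urologic surgery". No contact after discharge is described. Section 11 plans a comparison of similar surgeries and patients in SPSS and says nothing about differing time under observation.

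**The concern.** The end of observation for a yes/no event is the date of discharge. That date comes after randomisation, is a primary outcome in its own right, and is something the plan thinks treatment may change. Randomisation balances the patients but not the length of time for which they are watched. If the liposomal arm goes home sooner, its patients have fewer days in which constipation or ileus can be entered in the record, and the shortfall could be read as a bowel benefit.

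The reverse path is also open. Ileus can keep a patient in hospital, so fewer events may be a cause of the shorter stay and not a result of it. A finding of shorter stay with fewer events would fit an artefact of the window, a true bowel effect, or both, and data collected under this rule could not tell them apart.

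**Working it through.** **Inputs.** The plan gives no figure for this outcome to reproduce: no event rate, onset time or expected stay by arm. From section 6 there are 50 recruits and 10% attrition, so 50 × 0.9 = 45 evaluable, or 22.5 per arm if allocation is 1:1 (the ratio is not stated). Everything else below is an assumption. Each arm is given one fixed stay, 2 days in one and 3 days in the other, and true risk is the same in both.

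**Constant onset rate.** Let I be the true risk by day 3. The daily rate is h = −ln(1 − I)/3, and the proportion recorded by discharge is 1 − exp(−h × stay). For I = 0.30, h = 0.3567/3 = 0.1189. A 2-day stay gives 1 − exp(−0.2378) = 21.2%; a 3-day stay gives 30.0%.

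| True risk by day 3 | Recorded, 2-day stay | Recorded, 3-day stay | False gap (points) |
|---|---|---|---|
| 20% | 13.8% | 20.0% | 6.2 |
| 30% | 21.2% | 30.0% | 8.8 |
| 40% | 28.9% | 40.0% | 11.1 |

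At 22.5 per arm, 8.8 points is 0.088 × 22.5 = 2.0 patients.

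**Early onset.** Suppose 30% are ever affected and time to onset is exponential with mean m days. The proportion recorded is 0.30 × (1 − exp(−stay/m)).

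| Mean onset m | Recorded, 2-day stay | Recorded, 3-day stay | False gap (points) |
|---|---|---|---|
| 0.5 day | 29.5% | 29.9% | 0.5 |
| 1 day | 25.9% | 28.5% | 2.6 |
| 2 days | 19.0% | 23.3% | 4.3 |

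**What removes or cancels the gap.** With equal stays it is zero in either model. Under a constant rate, a true rate 3/2 = 1.5 times higher in the 2-day arm cancels the gap exactly, so the same window can also mask a real excess.

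**Reverse path.** If an event adds 2 days to the stay, an arm with risk p has its mean stay lengthened by 2p: 0.4 days at p = 0.20 and 0.6 days at p = 0.30. Two such arms would differ by 0.2 days in stay because of the events alone.

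**Fixed window.** With one window of W days from surgery and full capture, equal rates give 1 − exp(−hW) in both arms, and the false gap is zero. If only a share s of post-discharge events reaches the record, an arm with stay L shows F(L) + s × [F(W) − F(L)], where F is the cumulative risk. The gap is then (1 − s) × [F(3) − F(2)]. For the 8.8-point case and an assumed s = 0.5, that leaves 4.4 points. The fixed window removes the artefact in full only if post-discharge events are found as well as in-hospital ones.

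**The case against.** The strongest reply is that section 6 already reaches past discharge, because data come from the record "typically within 30 days of discharge from hospital". If that were follow-up to about 30 days after discharge, a one-day difference in stay would matter little. The phrase is loosely worded, but it more naturally says when the record is abstracted, and the sentence before it says when data are recorded. Even as follow-up it sets no common end point: a record pulled the day after discharge would comply.

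A second reply is that bowel events come early, so little is missed. That may be so: the gap is only 0.5 points if mean onset is half a day. But the documents give no onset times, and section 5 admits any urologic surgery, so stays may vary widely.

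Some stronger readings are tempting but not supported:

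- A reader might infer that the earlier-discharged arm must show fewer events whatever happens. It need not. Stays have to differ, some onset has to fall after the earlier discharge, and a higher true rate in that arm can cancel or reverse the gap.
- A reader might infer that the plan expressly excludes readmissions and later events. No sentence says so; it follows only from the time frame as worded.
- A reader might infer that the window hides a known harm of the test drug. Section 12 lists constipation among its commonest reactions but gives no comparison with the control. Section 8 describes adverse effects as similar to those of plain bupivacaine, which is the control.

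**Conclusion.** The concern holds as a conditional bias. Section 6 states a rule, section 13 expects that the stay may change, and nothing in sections 9 or 11 corrects for unequal observation. At equal true risk, with stays that differ and some onset after the earlier discharge, the expected recorded count is lower in the arm that leaves sooner. If that is the liposomal arm, the error favours it.

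The size cannot be fixed from the documents. For an assumed one-day difference (2 v 3 days), it runs from 0.5 points with very early onset to 11 points at a constant rate and 40% risk by day 3, and it is zero with equal stays. These figures treat stay as unaffected by the events; since ileus can lengthen stay, an observed difference could not be divided between artefact and effect. In about 45 patients this is a tendency and not a certain result, but it touches a primary outcome and is cheap to reduce.

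**What to change.** In section 6, count constipation and paralytic ileus over one fixed window from surgery, the same for every patient whatever the discharge date. Postoperative day 30 is one reasonable choice; a shorter fixed window also works. Either needs a stated reason. Take post-discharge events from clinic notes and readmissions in the medical record, and write a definition of each event that applies equally before and after discharge.

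State that the 30-day phrase is abstraction timing, and do not abstract before the window closes. For stays under 30 days, postoperative day 30 falls within 30 days of discharge. The margin is narrow: after a 2-day stay, day 30 is 28 days after discharge. The word for typical timing in section 6 leaves some room. Report in-hospital events with days at risk only as a secondary description.

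The cost is wording and later abstraction. The downside is that constipation at home is recorded less completely, and the arm discharged earlier spends more of its window there, so part of the gap can remain. If patients already attend a postoperative visit, one standard question put to all of them would limit this. It would be a small addition to data collection, because the documents describe no such visit.

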## **7. INFORMED CONSENT PROCESS**

Informed consent will be accomplished and signed at the Urology offices in the LLUMC or at the Urology FMO clinic. Consent will be obtained by the research coordinator or other trained investigators. Subjects will be randomly assigned as they are enrolled using a code system.

## **8. STUDY DESIGN**

Background or rationale for this study:

Liposomal bupivacaine was developed to extend the duration of efficacy of bupivacaine from the typical 6 - 8 hours up to 72 hours. The prolonged duration of liposomal bupivacaine was initially demonstrated in mice in 1994. Two randomized controlled trials using liposomal bupivacaine for bunionectomy and hemorhoidectomy resulted in FDA approval for its use in humans. More recently, liposomal bupivacaine has also been found to improve pain control for patients undergoing total knee arthroplasty. Infiltration of a local anesthetic into laparoscopic port sites is a common practice that has been shown in some studies to improve postoperative pain. Currently, no standard of care exists for postoperative pain and management is based on surgeon and anesthesiologist preferences. Liposomal bupivacaine has been one form of administered local, long-acting analgesia that

surgical centers have turned to. In addition, the analgesia has fewer adverse effects than opioids, with comparable adverse effects to those seen in bupivacaine alone.

Objectives: A prospective, randomized controlled study to determine the efficacy of liposomal bupivacaine given by local injection at all the wound sites in patients undergoing urologic surgeries.

Procedures involved (Research Interventions):

- The first group will receive intraoperative local Liposomal Bupivacaine injection at the surgical site.
- The control group will receive and will receive local Marcaine (bupivacaine HCl) injection.

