### **5. INCLUSION / EXCLUSION CRITERIA**

Inclusion criteria:

- Males or females 18-years-old or older.
- Undergoing urologic surgery.

Exclusion Criteria:

- Pregnant and/or nursing mothers.
- Allergy to bupivacaine.
- History of drug/alcohol abuse
- Severe cardiovascular, hepatic, renal disease or neurological impairment.

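### Initial analgesic orders may be chosen with the arm known, and most other perioperative analgesia is not listed for extraction or by-arm reporting

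*Combined protocol and SAP*

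**What the plan says.** **Treatment.** The only analgesic the protocol fixes is the study injection. For the test arm Section 8 states: "The first group will receive intraoperative local Liposomal Bupivacaine injection at the surgical site". The control arm receives plain bupivacaine in the same role. No other analgesia is specified for either arm. The background in Section 8 describes general practice this way: "Currently, no standard of care exists for postoperative pain and management is based on surgeon and anesthesiologist preferences". That is not a trial rule, but nothing later in the document replaces it.

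**Assignment and masking.** Section 7 states: "Subjects will be randomly assigned as they are enrolled using a code system". The text does not say whether the code conceals the arm from anyone. The only mention of double-blinding, in Section 12, concerns earlier studies of the product.

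**Outcomes.** Section 6 lists as primary "Total opioid consumption measured in intravenous morphine equivalents dose during the postoperative hospital Stay", postoperative pain scores and "Time to First Opioid Use", among others.

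**Data and analysis.** Section 6 states: "All data will be collected from the electronic medical record, typically within 30 days of discharge from hospital". Section 9 names the same source ("We will be using electronic medical records to retrieve data") and lists no variables. Section 11 bases the comparison on similar operations and similar patients, and does not mention co-analgesia.

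**The concern.** Randomisation balances clinician preferences that exist before assignment. It does not balance orders written afterwards by someone who knows the arm. A clinician who expects long-acting cover might omit a block or a patient-controlled opioid in the test arm. One who favours the new product might add non-opioids there. Either choice acts on three of the listed primary outcomes without passing through the study drug, and the direction cannot be predicted.

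This differs from extra analgesia given because a patient hurts, for example when plain bupivacaine wears off. That is a consequence of assignment and belongs in the treatment comparison. Unless the initial plan is written down before the arm is released, the two cannot be told apart afterwards.

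The second part is narrower. The opioid outcomes show how much postoperative opioid was given and when it began. They do not show which non-opioids, blocks or intraoperative opioid each arm received, or whether postoperative opioid was scheduled, patient-controlled or as-needed. A reader would want these to understand an opioid difference.

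**Working it through.** **1. What the text establishes.** Sections 6 and 8 fix the injection only. Section 7 puts assignment at enrolment. No section masks a prescriber or asks for the analgesic plan before the arm is released. So the route from knowledge of the arm to initial orders is open as written, but the text does not say that anyone will take it.

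**2. Inputs.** From Section 6: 50 recruited and 10% attrition, so 50 × 0.90 = 45 evaluable. The figure of 50 cannot be reproduced, because no alpha, power, effect size or SD is given. Everything below is assumed: 1:1 allocation (23 vs 22), two-sided 5% test, no true drug effect unless stated. No test is named in the plan.

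**3. Simple formula.** Bias in SD units = (difference in share given a co-analgesic) × (its effect in SDs). Standard error = √(2/22.5) = 0.298.
- Example, 20 points and 0.5 SD: bias = 0.20 × 0.5 = 0.10 SD; shift = 0.10/0.298 = 0.335; two-sided false-positive rate = Φ(0.335 − 1.96) + Φ(−0.335 − 1.96) = 0.052 + 0.011 = 6.3%, against 5%.
- For 10 to 50 points and 0.3 to 0.8 SD: bias 0.03 to 0.40 SD; false-positive rate 5.1% to 26.9%.
- Reverse direction: the detectable difference at 80% power is (1.96 + 0.842) × 0.298 = 0.84 SD. Power for that true effect falls from 80% to between 77% and 31%.

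**4. Total opioid, simulated.** Lognormal totals, t-test on the log scale, 40% use of the co-analgesic in the lower-use arm, opioid use cut by 20%, 30% or 50%, 20-point imbalance. The table gives the rate of a significant result favouring the test arm; balanced arms give about 2.5%.

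| Assumed CV | Test arm gets more | Control gets more |
|---|---|---|
| 60–80% | about 4–10% | about 0.3–1.4% |
| 120–150% | about 3–7% | about 0.9–1.8% |

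The wider CV is plausible because Section 5 requires only "Undergoing urologic surgery". At that CV the two-sided rate is about 5–8%, against 5%.

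**5. Time to first opioid, simulated.** Scheduled or patient-controlled opioid starts within the first hour in 30%, 40% or 60% of controls. All other patients have exponential times with median 2, 4 or 8 hours, cut at 48 hours; rank test. If early starts are 10 points less frequent in the test arm, the false favourable rate is about 6–8%; at 20 points less frequent, about 12–18%. In the reverse direction it is below 1%.

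**6. Prescribers masked.** There is no bias, only extra spread. With 40% use in both arms, the variance of log opioid rises by 0.24 × [ln(1 − r)]² / ln(1 + CV²), where r is the opioid reduction.
- CV 1.5, r 0.2: 0.24 × 0.0498/1.179 = 1.0%.
- CV 0.6, r 0.5: 0.24 × 0.480/0.307 = 37.5%.
- At CV 1.2–1.5 the range is 1–13%.

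**7. What a by-arm table can show.** With 40% use in both arms, chance alone gives an imbalance of 20 points or more in about 17% of trials this size. For 60% vs 40%, the 95% half-width is 1.96 × √(0.24/23 + 0.24/22) = 28.6 points.

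Pain scores were not quantified.

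**The case against.** - **The bias depends on masking, and the text does not say prescribers are unmasked.** This stands. A reader might infer that the arms will be treated differently, or that the trial is open-label. The documents support neither inference: the code system could be masked or not. The point is that nothing closes the route.
- **Postoperative opioid is already captured.** This stands. A reader might infer that scheduled or patient-controlled opioid goes uncounted. Section 6 makes the in-hospital total and the time to first opioid outcomes, so every postoperative dose counts whatever the order type. Only the order-type label is missing.
- **Clinician-chosen analgesia is acceptable in a Phase IV trial.** This stands, and no common regimen is asked for. It also rules out the stronger claim that the opioid result could not be interpreted without co-analgesia data. Total opioid by assigned arm under usual care is a valid comparison; the extra data help to explain it.
- **Section 9 lists no fields at all.** This is true, so the omission reflects a short outline rather than a decision to leave co-analgesia out. Even so, presence in the record commits nobody to extract or report it.
- **The figures are assumed, and the largest depend on the inputs.** This stands. The 12–18% requires early starts within the hour and a 20-point gap due to knowledge of the arm. For opioid total at a wide CV the effect is modest.
- **A table only documents the problem.** This is largely true, which is why the release step is the main fix and the table supports it.

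**Conclusion.** The concern holds in conditional form. As written, the plan lets initial analgesic orders be chosen with the arm known, and such orders could move total opioid use, pain scores and time to first opioid in either direction. If prescribers are masked, that bias is absent and only extra variance remains.

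The documents give no basis for a size. The illustrations suggest a small to moderate effect on opioid total and a larger one on time to first opioid if early scheduled or patient-controlled starts differ by arm. These results rest on the assumed imbalances, co-analgesic effects and variability set out above.

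Separately from masking, non-opioid analgesics, blocks, intraoperative opioid and postoperative order type are not listed for extraction or by-arm reporting. That limits how well a result can be explained; it does not invalidate the comparison.

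**What to change.** **Main change (Sections 7 and 8).** Release the assignment to the surgeon and anesthesiologist only after each patient's planned perioperative analgesia has been recorded. The content stays their clinical choice. Departures are allowed, including for safety reasons such as total local anesthetic dose, and are recorded with the reason.

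**Supporting change (Sections 9 and 11).** Extract non-opioid analgesics, blocks, intraoperative opioid, and whether each postoperative opioid was scheduled, patient-controlled or as-needed. Report these by arm, with the type of first opioid, as description without significance tests. Do not adjust the main comparison for analgesia given after the arm is known. Keep time to first opioid as first use of any postoperative opioid.

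**Cost and limits.** One form line and a later release step per patient, a few more fields from a record already being read, and one table. Sample size and clinical care do not change. The release step protects only the initial plan; later ward orders are documented, not prevented. With about 45 patients the table cannot reliably separate a 20-point imbalance from chance.
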